 - To interrupt therapy immediately if an infection develops, and to immediately report any symptoms indicative of infection such as fever, sore throat, or flu-like symptoms. In presence of confirmed fever and/or infection, they will be required to have their neutrophil counts tested as soon as possible and no later than 24 hours after the symptoms of infection are detected.
 - o If patient decides to leave the study before completion, to return to the clinic for an Early Termination Visit as soon as possible, and no later than 1 month following the last dose of study medication
- Provide patient or authorized legal representative with an emergency card, and advise her/him to carry this card at all times
- Schedule next study visit

Regular Blood Draws

Notes:

- o These blood draws can be conducted either at a local laboratory or at the study site.
- o For patients in Group 1, the blood draws will be done monthly. For patients in Group 2, they will be done weekly for the first 6 months (up to Week 26), biweekly for the next 6 months (up to Week 52), and monthly thereafter. In all cases, the window is \pm 3 days.
- Collect blood sample for hematology. Hematology results should be reviewed by the investigator as soon as they are received from the laboratory (within 24 hours if possible).
- If the patient receives a blood transfusion (either at one of these visits or at any other time during the study), record the type of transfusion (simple, exchange, partial

exchange; and if exchange or partial exchange, what was the volume of blood removed and the average mean hematocrit of the packed red blood cells removed), volume of blood that the patient received during the transfusions, and the mean hematocrit of the packed red blood cell units transfused (data obtained from the site's blood bank).

Visit 2 (Week 13 ± 7 days)

- Review patient diary card, and file it with the source documents
- Document information on adverse events, use of concomitant medications, and treatment compliance
- Collect blood samples for the following assessments:
 - Hematology
 - Serum ferritin

Pregnancy

- o testing for all females of childbearing potential. A negative result is required for study continuation.
- Measure vital signs and weight

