7.2.1.8 Adverse Events of Special Interest

7.2.1.8.1 Neutropenia

Patients taking deferiprone must be monitored for neutropenia, defined as a confirmed absolute neutrophil count (ANC) less than 1.5×10^9 /L. Categories of neutropenia are as follows:

• Mild: A confirmed ANC $< 1.5 \times 10^9/L \text{ but } \ge 1.0 \times 10^9/L$

• Moderate: A confirmed ANC $< 1.0 \times 10^9/L \text{ but} \ge 0.5 \times 10^9/L$

• Severe: A confirmed ANC $< 0.5 \times 10^9$ /L. Severe neutropenia is also

referred to as agranulocytosis.

For a case of neutropenia to be confirmed, there must be 2 consecutive counts, a maximum of 3 days apart, that are both less than the specified value. If both counts are below 1.5×10^9 /L but are not in the same severity category, a third count will be required to determine the severity.

The management of different severities of neutropenia is described below. In addition to having ANC monitored, patients or authorized legal guardians will be advised to immediately report any symptoms indicative of infection such as fever, sore throat, and flulike symptoms; and will be provided with an emergency services card with contact information which they are advised to carry with them at all times. In presence of confirmed fever and/or infection, they will be required to have their neutrophil counts tested as soon as possible and no later than 24 hours after the symptoms of infection are detected.

Mild neutropenia: The patient should continue deferiprone treatment, and ANC will be monitored every 2 days until resolution of the event, defined as 2 consecutive ANC ≥ 1.5 x 10^9 /L. If ANC is still < 1.5 x 10^9 /L after 14 days, the investigator is to do the following:

- Withdraw patient from the study and monitor him/her until resolution of the event
- Advise patient regarding protective isolation
- Examine patient the same day (if possible), including drug history and physical examination
- Notify ApoPharma Inc. by fax

If a patient with mild neutropenia develops an infection, deferiprone therapy must be interrupted immediately, and neutrophil count will continue to be monitored every 2 days

until resolution. Therapy can be re-initiated once all symptoms have been resolved and it is deemed safe by the investigator.

Moderate neutropenia: Patient will immediately interrupt treatment, and ANC will be monitored every 2 days until resolution of the event. If ANC is still $< 1.5 \times 10^9$ /L after 14 days, the investigator is to do the following:

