
- Withdraw patient from the study and monitor him/her until resolution of the event
- Provide protective isolation; if clinically indicated, admit patient to hospital and obtain vital signs every 4 hours
- Examine the patient the same day, if possible, including drug history and physical examination
- If possible, obtain viral studies (CMV, parvovirus, hepatitis A/B/C), serum ALT, BUN, creatinine, and 10 mL serum split into two 5-mL aliquots for frozen storage, for future analysis
- Notify ApoPharma Inc. by fax

Severe neutropenia/agranulocytosis: Patient will immediately discontinue treatment and will be permanently withdrawn from the study, and ANC will be monitored daily until resolution of the event. The following procedures should be done by the investigator or the treating physician, as appropriate:

- Provide protective isolation; if clinically indicated, admit patient to hospital and obtain vital signs every 4 hours
- Examine the patient the same day, if possible, including drug history and physical examination
- If possible, obtain viral studies (CMV, parvovirus, hepatitis A/B/C), serum ALT, BUN, creatinine, and 10 mL serum split into two 5-mL aliquots for frozen storage
- With the patient's consent, collect a blood sample to attempt to identify genetic or other biomarkers related to agranulocytosis (refer to the operations manual for further instructions)
- If possible, consider obtaining bone marrow aspirate for:
 - Histology
 - Progenitor culture

- o Frozen storage (1 mL sample)
- If possible, consider obtaining bone marrow biopsy (minimum length 3 mm)
- Perform septic work-up including chest X-ray, blood, urine and throat cultures
- Obtain q4h temperatures from patient (monitored by family at home if patient is not in the hospital)
- If warranted, administer granulocyte stimulating factors, such as G-CSF 10 μ g/kg, as an inpatient if possible, beginning the same day that the ANC is confirmed as < 0.5 x 10^9 /L; administer daily until ANC is > 1.5 x 10^9 /L on 2 consecutive days
- If ANC $< 0.5 \times 10^9$ /L for 7 days, repeat bone marrow biopsy and aspirate weekly during the period of agranulocytosis, if warranted
- Notify ApoPharma Inc. by [contact] Infections

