6.3.4 Analysis of Safety

The incidences of AEs and SAEs reported from the start of deferiprone therapy for all patients will be tabulated. For patients continuing on deferiprone, this time period will be from the start of LA38-0411 to the completion of LA38-EXT; for those switching to deferiprone, it will be from the start of LA38-EXT to the completion of LA38-EXT. AEs will be summarized by worst severity and by relationship to the study medication. Time to onset and duration of all SAEs, of AEs of special interest such as neutropenia, agranulocytosis, increased ALT, and arthralgia: 1) the mean time to the first onset and the mean time to the last recurrence will be calculated, and 2) the mean duration for the first episode and the mean duration for any recurrent episodes, excluding the first episode, will be calculated for all SAEs and AEs of special interest.

The percentage of discontinuations due to AEs will be calculated, and the AEs leading to discontinuation will be summarized in a frequency table.

Laboratory data (hematology and chemistry) will be summarized using descriptive statistics for continuous variables and frequency tables for discrete variables. The incidences of out-of-range data will be tabulated, and the changes from baseline to the end of study will be presented in shift tables.

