14.3.6 Laboratory Data

14.3.6.1 Hematology

Table 14.3.6.1.1 Hemoglobin at each assessment – Safety population

Table 14.3.6.1.2 Change in hemoglobin from baseline to each follow-up assessment – Safety population

Table 14.3.6.1.3 Shift table for hemoglobin in abnormal range at baseline vs. last assessment – Safety population

Note: Similar tables will be produced for total white blood cell (WBC), absolute neutrophil count (ANC), and platelets.

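### Baseline-to-last laboratory shift tables cannot show a neutropenia or ALT rise that resolved before the last sample; add baseline-to-worst tables beside them

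*SAP*

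**What the plan says.** **Shift tables.** SAP section 6.3.4 states that "the changes from baseline to the end of study will be presented in shift tables". The table list in SAP section 14.3.6.1 has the same form, "Shift table for hemoglobin in abnormal range at baseline vs. last assessment", and adds that "Similar tables will be produced for total white blood cell (WBC), absolute neutrophil count (ANC), and platelets". Section 14.3.6.2 does the same for biochemistry, with ALT and AST among the analytes. The shells (Tables 14.3.6.1.3 and 14.3.6.1.4, 14.3.6.2.3 and 14.3.6.2.4) cross Low, Normal and High at baseline with the same classes at the last assessment. No shift table uses a worst post-baseline value, and neither document defines last assessment.

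**Neutropenia follow-up (Protocol 7.2.1.8.1).**
- Mild: deferiprone continues, with counts every 2 days "until resolution of the event, defined as 2 consecutive ANC" of at least 1.5 x 10^9/L.
- Moderate: "Patient will immediately interrupt treatment, and ANC will be monitored every 2 days until resolution of the event". Protocol 4.5.3 allows a restart after recovery.
- Mild or moderate, still below 1.5 x 10^9/L after 14 days: the patient is withdrawn.
- Severe (agranulocytosis): the patient is "permanently withdrawn from the study, and ANC will be monitored daily until resolution of the event".

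**Early termination.** Under Protocol 5.1, patients who leave early "return to the clinic for an Early Termination Visit as soon as possible, and no later than 1 month" after the last dose. Hematology is part of that visit.

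**The concern.** Safety is the primary objective, and neutropenia, agranulocytosis and increased ALT are named as events of special interest. A shift table is the display a reader turns to for worsening from baseline that does not depend on whether the investigator reported an event. If it uses only the last value, a patient whose ANC fell and recovered appears as Normal to Normal, exactly like a patient whose ANC never moved.

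The independence matters. Under Protocol 7.2.1.1 and 7.2.2, an abnormal laboratory value becomes an adverse event only if the investigator judges it clinically significant. The laboratory tables are the check on that judgement, and the planned shift tables cannot provide it for transient abnormalities.

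**Working it through.** **Step 1. Which episodes does the last value miss?** Setting the follow-up rules against the table definition:

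| Episode | What the protocol allows next | Likely position of the last count |
|---|---|---|
| Mild, resolved within 14 days | Stays on study, up to Week 104 | After recovery, possibly by months |
| Moderate, resolved within 14 days | May restart and stay on study | After recovery, possibly by months |
| Mild or moderate, still below 1.5 x 10^9/L at 14 days | Withdrawn, monitored to resolution | Before or after recovery |
| Severe | Withdrawn, counted daily to resolution | Before or after recovery |

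In the first two rows the patient would normally appear as Normal to Normal. In the last two, the result depends on whether last assessment means the Early Termination count or a later follow-up count. It also depends on the data source: the hematology shift table draws on Listing 16.2.9, while local laboratory results have their own Listing 16.2.25. Low is not tied to a stated ANC cut-off either.

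For ALT the logic is the same but weaker. Biochemistry is semi-annual (Protocol 7.2.2), interruption is at the investigator's discretion (Protocol 4.5.3), and no ALT-specific serial monitoring to recovery is required. A rise that settles before the last sample is missed, but the protocol does not make recovery the expected state.

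**Step 2. Do the other laboratory outputs fill the gap?** Only in part.
- Out-of-range incidence is promised in SAP 6.3.4, but sections 14.3.6.1 and 14.3.6.2 list no table for it. The SAP also drops the condition in Protocol 9.4.1.4 that the abnormality be seen on two consecutive measures.
- The by-visit ANC tables (same grid as Tables 14.3.6.1.1 and 14.3.6.1.2) have weekly rows to Week 51, then Month 12 and quarterly rows to Month 36. There is no row for every-2-day or daily counts.
- The figure of proportion abnormal (Figure 14.3.1.2 and its ANC counterpart) is by assessment and does not link a patient's low count to baseline.

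**Step 3. Scale.** Inputs from Protocol 1.3: agranulocytosis 15 of 712, neutropenia 49 of 712. Rates: 15/712 = 2.11% and 49/712 = 6.88%, matching the printed 2.1% and 6.9%. Protocol 4.1 gives 300 planned patients in the parent study, and Protocol 1.2 gives 2:1 allocation, so Group 2 is at most 300 x 1/3 = 100.

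- Expected cases = N x rate. Per 100: 2.1 and 6.9. Per 300: 6.3 and 20.6.
- Chance of at least one agranulocytosis = 1 - (1 - 0.0211)^N: 0.88 for N = 100 and 0.998 for N = 300.

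If s is the share of cases whose last count is back to Normal, and baseline is Normal, the number still shown as Low is N x rate x (1 - s):

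| s | Agranulocytosis, per 100 / 300 | Neutropenia, per 100 / 300 |
|---|---|---|
| 0% | 2.1 / 6.3 | 6.9 / 20.6 |
| 50% | 1.1 / 3.2 | 3.4 / 10.3 |
| 90% | 0.2 / 0.6 | 0.7 / 2.1 |
| 100% | 0 / 0 | 0 / 0 |

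The documents do not fix s. Only its direction is clear, and it should be high for mild and moderate episodes that recover within 14 days.

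**The case against.** The strongest reply is that the shift table is not the main display for these events. SAP 6.3.4 plans incidence of adverse and serious adverse events. It also plans time to first onset, time to last recurrence and duration for neutropenia, agranulocytosis and increased ALT by name (Tables 14.3.1.10, 14.3.1.12, 14.3.1.14 and 14.3.1.16). Withdrawals due to adverse events appear in Table 14.3.1.1 and Listing 16.2.28. The by-visit tables give minimum and maximum. Protocol 9.4.1.4 itself specifies baseline-to-end-of-study shift tables, so the SAP follows the protocol. All of this stands. It makes the remedy an addition rather than a replacement, and it rules out reading the plan as concealment.

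A reader might also infer that agranulocytosis, the gravest case, is shown as normal by design, so that almost none of the expected cases would appear as Low. The documents do not support that. Agranulocytosis forces withdrawal, the Early Termination visit is to be held as soon as possible, and its count may precede recovery. Near-zero counts are the 100% row of the table above, not a result.

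A further fair point is that worst values depend on how often counts are taken, and the two groups have different schedules. A Low/Normal/High table of worst values would also put an ANC of 1.4 in the same cell as 0.2, so the added table needs finer categories.

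What the reply does not answer is that the adverse event outputs rest on investigator judgement and that the one promised laboratory summary independent of the last value has no listed table.

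**Conclusion.** The point holds as a gap in objective laboratory reporting. The planned shift tables cannot show an abnormality that resolved before the last sample. The loss is most likely for mild and moderate neutropenia recovering within 14 days. It is uncertain for agranulocytosis, because last assessment is undefined. It is possible but not built in for ALT.

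The size is modest. At the rates in Protocol 1.3, about 2 agranulocytosis and 7 neutropenia cases per 100 patients, or 6 and 21 per 300, are at issue, and the number missed runs from none to all of them according to the share resolved. This assumes that the earlier trials' rates apply and that baseline ANC is normal. The 300 is a ceiling, since the extension's own sample size is not stated and only parent-study completers may enter. Group 1 may differ after a year on drug, as Protocol 1.3 says agranulocytosis peaks at 5 months and then declines.

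This is a cheap and worthwhile improvement for a study whose primary objective is safety. It does not undermine the safety analysis as a whole.

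**What to change.** 1. Keep the baseline-to-last tables, and define last assessment: which visit or follow-up count, and from which listings.
2. Add baseline-to-worst post-baseline shift tables, running from the first deferiprone dose through follow-up and including unscheduled counts and local-laboratory counts (Listing 16.2.25).
3. Show ANC in the protocol's confirmed categories: at least 1.5, 1.0 to below 1.5, 0.5 to below 1.0, and below 0.5 x 10^9/L. State how a single unconfirmed low count is handled.
4. Use the lowest value for WBC, platelets and hemoglobin, and the highest for ALT and AST.
5. List a numbered table for the out-of-range incidence, and say whether the protocol's two-consecutive-measures condition applies.

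No new data collection is needed. The cost is SAP wording and extra programming, and the note at the head of SAP section 14 already allows for added tables. The downsides are that more abnormal shifts will be shown and that worst values depend on count frequency, which differs between Group 1 and Group 2. The new tables should therefore be read within group and placed beside the baseline-to-last tables.

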14 SUMMARY TABLES AND FIGURES

Note: The final numberings for tables and/or figures in the clinical study report can be changed if more tables and/or figures are added in addition to those in the SAP.

TABLES

14.1 Disposition, Demographics and Baseline Data

Table 14.1.1 Patient disposition

Table 14.1.2 Number of patients in the ITT, PP, and safety populations

Table 14.1.3 Number of patients by study site

Table 14.1.4 Reasons for not completing the study

Table 14.1.5 Demographics data

Table 14.1.6 LIC, cardiac MRI T2*, serum ferritin at baseline

Table 14.1.7 Medical history

Table 14.1.8 Vital signs at baseline

Table 14.1.9 Weight and height at baseline

14.2 Efficacy Analyses

14.2.1 LIC

Table 14.2.1.1 LIC at each assessment

Table 14.2.1.2 Change in LIC at each follow-up assessment

Table 14.2.1.3 Change in LIC for DFO+DFP group – Data from the extension study

Table 14.2.1.4 Change in LIC for DFO and DFO+DFP group

Table 14.2.1.5 Responder analysis in LIC defined as $\geq 20\%$ decline in LIC from baseline

Table 14.2.1.6 Responder analysis in LIC defined as $\geq 20\%$ decline in LIC from baseline for DFO+DFP group – Data from the extension study

14.2.2 Cardiac MRI T2*

Table 14.2.2.1 Cardiac MRI T2* at each assessment

Table 14.2.2.2 Change cardiac MRI T2* at each follow-up assessment

Table 14.2.2.3 Change in cardiac MRI T2* for DFO+DFP group – Data from the extension Study

Table 14.2.2.4 Change in cardiac MRI T2* for DFO and DFO+DFP group

Table 14.2.2.5 Responder analysis in cardiac MRI T2* defined as $\geq 20\%$ increase in cardiac MRI T2* from baseline

Table 14.2.2.6 Responder analysis in cardiac MRI T2* defined as $\geq 20\%$ increase in cardiac MRI T2* baseline for DFO+DFP group – Data from the extension study

14.2.3 Serum Ferritin

Table 14.2.3.1 Serum ferritin at each assessment

Table 14.2.3.2 Change in serum ferritin at each follow-up assessment

Table 14.2.3.3 Change in serum ferritin for DFO+DFP group – Data from the extension study

Table 14.2.3.4 Responder analysis in serum ferritin defined as $\geq 20\%$ decline in serum ferritin from baseline

Table 14.2.3.5 Responder analysis in serum ferritin defined as $\geq 20\%$ decline in serum ferritin from baseline for DFO+DFP group – Data from the extension study

14.3 Safety Analyses

14.3.1 Adverse Events

Table 14.3.1.1 Overall summary of adverse events – Safety population

Table 14.3.1.2 Summary of adverse events – Safety population

Table 14.3.1.3 Summary of most common adverse events ($\geq 5\%$ in total) – Safety population

Table 14.3.1.4 Summary of adverse drug reactions – Safety population

Table 14.3.1.5 Summary of most common adverse drug reactions ($\geq 5\%$ in total) – Safety population

Table 14.3.1.6 Summary of serious adverse events – Safety population

Table 14.3.1.7 Summary of serious adverse drug reactions – Safety population

Table 14.3.1.8 Summary of adverse events by causality – Safety population

Table 14.3.1.9 Time to the first onset of SAEs – Safety population

Table 14.3.1.10 Time to the first onset of AEs of special interest such as neutropenia, agranulocytosis, increased ALT, arthralgia – Safety population

Table 14.3.1.11 Time to the last recurrence of SAEs – Safety population

Table 14.3.1.12 Time to the last recurrence of AEs of special interest such as neutropenia, agranulocytosis, increased ALT, arthralgia – Safety population

Table 14.3.1.13 Duration of the first onset of SAEs – Safety population

Table 14.3.1.14 Duration of the first onset of AEs of special interest such as neutropenia, agranulocytosis, increased ALT, arthralgia – Safety population

Table 14.3.1.15 Duration of the last recurrence of SAEs – Safety population

Table 14.3.1.16 Duration of the last recurrence of AEs of special interest such as neutropenia, agranulocytosis, increased ALT, arthralgia – Safety population

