The most common adverse reactions (adverse events assessed as at least possibly related to deferiprone use) seen among the 712 patients treated with deferiprone in ApoPharma clinical trials carried out for the indication of systemic iron overload are listed in the table below. For detailed information on adverse events (AEs) associated with deferiprone, see the Investigator's Brochure. (16)

Adverse drug reactions occurring in $\geq 1\%$ of 712 deferiprone-treated patients

System Organ Class	Patients	
Preferred Term	n (%)	
Blood and lymphatic system disorders		
Neutropenia	49 (6.9)	
Agranulocytosis	15 (2.1)	
Gastrointestinal disorders		
Nausea	89 (12.5)	
Vomiting	69 (9.7)	
Abdominal pain upper	39 (5.5)	
Abdominal pain	23 (3.2)	
Diarrhoea	21 (2.9)	
Dyspepsia	13 (1.8)	
Abdominal discomfort	10 (1.4)	
Investigations		
Alanine aminotransferase increased	54 (7.6)	
Neutrophil count decreased	50 (7.0)	
Weight increased	12 (1.7)	
Aspartate aminotransferase increased	11 (1.5)	
Metabolism and nutrition disorders		
Increased appetite	26 (3.7)	
Decreased appetite	8 (1.1)	
Musculoskeletal and connective tissue disorders		
Arthralgia	75 (10.5)	
Back pain	13 (1.8)	
Pain in extremity	12 (1.7)	
Arthropathy	9 (1.3)	
Nervous system disorders		
Headache	17 (2.4)	
Renal and urinary disorders		
Chromaturia	95 (13.3)	

Data cut-off date: 31 August 2014

Currently, deferoxamine and deferasirox are the only iron chelators licensed for use in patients with sickle cell disease. The benefit to participants in this trial is that they will have the option of being treated with a third chelator.

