7.2.1.4 Assessment of Intensity

Intensity refers to the degree of discomfort or impairment associated with an event. The intensity of AEs is to be reported on the CRF as mild, moderate, or severe, according to the definitions provided below. In addition, to maximize consistency in assessment, it is recommended that the National Cancer Institute (NCI) Common Terminology Criteria for Adverse Events (CTCAE) scale be used.

Intensity	Corresponding NCI CTCAE Grade
Mild: awareness of a sign or symptom but easily tolerated	1
Moderate : discomfort sufficient to cause interference with normal daily activities	2
Severe : resulting in inability to do work or perform normal daily activities	3–5

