7.2.2 Laboratory Measurements

Analyses will be performed at a central laboratory, with the exception of the weekly, biweekly, or monthly hematology assessments which may be performed at a local laboratory. Investigators must interpret each report promptly (preferably within 24 hours) and must document their review by signing or initialing and dating it. Any laboratory values that fall outside a clinically accepted range, or values that differ significantly from previous values, must be assessed for clinical significance, and must be marked by the investigator as either "CS" (clinically significant) or "NCS" (not clinically significant). Any clinically significant abnormalities or changes that are not part of a larger medical condition that is already

recorded must be further explained on the laboratory report and documented as an adverse event in the eCRF.

The following laboratory tests will be performed:

- **Hematology** (for Group 1, monthly throughout the study; for Group 2, weekly for the first 6 months, biweekly for the next 6 months, and monthly thereafter): hemoglobin, total WBC count, ANC, and platelet count
- **Biochemistry** (semi-annually; Visits 1, 3, 5, 7, and 9): total protein, GGT, lactate dehydrogenase (LDH), sodium, potassium, chloride, fasting glucose, total and direct bilirubin (indirect bilirubin will be calculated by the sponsor), AST, ALT, albumin, blood urea nitrogen, calcium, creatinine, uric acid, alkaline phosphatase, and amylase
- Serology (Visits 1 and 9): Hepatitis B and C and HIV testing
- **Urinalysis** (annually; Visits 1, 5, and 9): pH, specific gravity, glucose, protein, ketones, blood, and (if indicated by the dipstick results), sediment microscopy. If there is blood in the urine or three or more "plus signs" for protein, samples must be sent for microscopy.
- **Pregnancy** (quarterly; Visits 1–9): serum pregnancy test

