5.2.3 Adverse Events of Special Interest

5.2.3.1 Neutropenia

Patients taking deferiprone were monitored for neutropenia, defined as a confirmed absolute neutrophil count (ANC) less than $1.5 \times 10^9/L$. Categories of neutropenia are as follows:

- Mild: A confirmed ANC $< 1.5 \times 10^9/L$ but $\geq 1.0 \times 10^9/L$
- Moderate: A confirmed ANC $< 1.0 \times 10^9/L$ but $\geq 0.5 \times 10^9/L$
- Severe: A confirmed ANC $< 0.5 \times 10^9/L$. Severe neutropenia is also referred to as agranulocytosis.

For a case of neutropenia to be confirmed, there must be 2 consecutive counts, a maximum of 3 days apart, that are both less than the specified value. If both counts are below $1.5 \times 10^9/L$ but are not in the same severity category, a third count was required to determine the severity.

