16.2 Patient Data Listings

- 16.2.1 Listing of informed consent
- 16.2.2 Listing of demographics
- 16.2.3 Listing of primary diagnosis
- 16.2.4 Listing of transfusion history
- 16.2.5 Listing of vital signs including height, weight
- 16.2.6 Listing of physical examination
- 16.2.7 Listing of 12-lead electrocardiogram
- 16.2.8 Listing of urinalysis
- 16.2.9 Listing of hematology
- 16.2.10 Listing of LIC
- 16.2.11 Listing of cardiac MRI T2*
- 16.2.12 Listing of chemistry
- 16.2.13 Listing of serology
- 16.2.14 Listing of pregnancy
- 16.2.15 Listing of urine microscopy
- 16.2.16 Listing of serum ferritin
- 16.2.17 Listing of dose verification
- 16.2.18 Listing of disposition
- 16.2.19 Listing of compliance
- 16.2.20 Listing of medical history
- 16.2.21 Listing of medication
- 16.2.22 Listing of medical events
- 16.2.23 Listing of adverse events
- 16.2.24 Listing of exposure
- 16.2.25 Listing of local labs
- 16.2.26 Listing of transfusion information
- 16.2.27 Listing of SAEs
- 16.2.28 Listing of withdrawals due to AEs

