System Organ Class Preferred Term		n Patients (%)	n Patients (%)	P-value (Fisher's exact test)
CCCCCCC		x (x.x)	x (x.x)	0xxxx
Cccccc		x (x.x)	x (x.x)	0xxxx
Ccccccc		x (x.x)	x (x.x)	0xxxx
Ccccccc		x (x.x)	x (x.x)	0xxxx
.....	

Note: Similar tables will be produced from Table 14.3.1.3 to Table 14.3.1.7

Data source: 16.2.23 Listing of adverse events

Table 14.3.1.8 Adverse events by causality

		Treatment	
		DFP+DFP (N=xxx)	DFO+DFP (N=xxx)
System Organ Class Preferred Term	Relatedness (worst case)	Patients reporting (n=xx)	Patients reporting (n=xx)
CCCCCCCC		x (x.x)	x (x.x)
cccccc	Not Related*	x (x.x)	x (x.x)
	Related**	x (x.x)	x (x.x)
cccccc	Not Related	x (x.x)	x (x.x)
	Related*	x (x.x)	x (x.x)
.....

*Not related

**Possibly, Probably, or Definitely Related

Data source: 16.2.23 Listing of adverse events

Table 14.3.1.9 Time to the first onset of SAEs

	Treatment				
	DFP+DFP		DFO+DFP		
SAE	N	Mean ± SD (Min, Max)	N	Mean ± SD (Min, Max)	P-value (T-test)
Ccccccc	XXX	xx.x ± xx.x (xx, xx)	XXX	xx.x ± xx.x (xx, xx)	0xxxx
Ccccccc	XXX	xx.x ± xx.x (xx, xx)	XXX	xx.x ± xx.x (xx, xx)	0xxxx
....	XXX	xx.x ± xx.x (xx, xx)	XXX	xx.x ± xx.x (xx, xx)	0xxxx
Ccccccc	XXX	xx.x ± xx.x (xx, xx)	XXX	xx.x ± xx.x (xx, xx)	0xxxx

Note: Similar table will be produced for Table 14.3.1.10.

Data source: 16.2.23 Listing of adverse events

Table 14.3.1.11 Time to the last recurrence of SAEs

	Treatment				
	DFP+DFP		DFO+DFP		
SAE	N	Mean ± SD (Min, Max)	N	Mean ± SD (Min, Max)	P-value (T-test)
Ccccccc	XXX	xx.x ± xx.x (xx, xx)	Xxx	xx.x ± xx.x (xx, xx)	0xxxx
Ccccccc	XXX	xx.x ± xx.x (xx, xx)	Xxx	xx.x ± xx.x (xx, xx)	0xxxx
....	XXX	xx.x ± xx.x (xx, xx)	Xxx	xx.x ± xx.x (xx, xx)	0xxxx
Ccccccc	XXX	xx.x ± xx.x (xx, xx)	Xxx	xx.x ± xx.x (xx, xx)	0xxxx

Note: Similar table will be produced for Table 14.3.1.12.

Data source: 16.2.23 Listing of adverse events

Table 14.3.1.13 Duration of the first onset of SAEs

		Treatment			
		DFP+DFP		DFO+DFP	
SAE	N	Mean \pm SD (Min, Max)	N	Mean \pm SD (Min, Max)	P-value (T-test)
Ccccccc	XXX	XX.X \pm XX.X (xx, xx)	XXX	XX.X \pm XX.X (xx, xx)	0.xxxx
Ccccccc	XXX	XX.X \pm XX.X (xx, xx)	XXX	XX.X \pm XX.X (xx, xx)	0.xxxx
....	XXX	XX.X \pm XX.X (xx, xx)	XXX	XX.X \pm XX.X (xx, xx)	0.xxxx
Ccccccc	XXX	XX.X \pm XX.X (xx, xx)	XXX	XX.X \pm XX.X (xx, xx)	0.xxxx

Note: Similar table will be produced for Table 14.3.1.14.

Data source: 16.2.23 Listing of adverse events

Table 14.3.1.15 Duration of the last recurrence of SAEs

		Treatment			
		DFP+DFP		DFO+DFP	

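### Neutropenia is defined by confirmed ANC, but its special-interest tables are built from reported AE terms, so mild and moderate cases may be missed or mistimed

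*SAP*

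**What the plan says.** **Definition.** SAP 5.2.3.1, under the heading for adverse events of special interest, states: "Patients taking deferiprone were monitored for neutropenia, defined as a confirmed absolute neutrophil count (ANC) less than" 1.5 x 10^9/L. Mild, moderate and severe are separated at 1.0 and 0.5, and severe neutropenia is agranulocytosis. To confirm a case, "there must be 2 consecutive counts, a maximum of 3 days apart, that are both less than the specified value". If the two counts fall in different categories, a third decides. Protocol 7.2.1.8.1 gives the same rule.

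**Analysis.** SAP 6.3.4 asks for mean time to first onset, mean time to last recurrence, and mean durations of special-interest events. SAP 14.3.1 assigns these to Tables 14.3.1.10, .12, .14 and .16, the first being "Time to the first onset of AEs of special interest such as neutropenia, agranulocytosis, increased ALT, arthralgia". In SAP 17 these tables follow the SAE shells, with one row per event term and the footnote "Data source: 16.2.23 Listing of adverse events".

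**How a low count reaches that listing.** Under Protocol 7.2.1.1, a laboratory abnormality is an AE when the investigator judges it clinically significant. Under Protocol 7.2.2, values outside the accepted range "must be assessed for clinical significance, and must be marked by the investigator as either" clinically significant or not, and the significant ones are documented as AEs.

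**Terms in use.** The pooled table in Protocol 1.3 has separate rows for neutropenia, for agranulocytosis and, under Investigations, for "Neutrophil count decreased".

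**The concern.** The study has an objective, count-based definition of its main haematological risk, and the tables meant to describe that risk do not use it. What they show depends on two steps outside the definition: whether the investigator calls the count clinically significant, and which preferred term the event is coded to.

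Safety is the primary objective, and AE frequency, onset and duration are primary endpoints (SAP 6.1.1). If a confirmed episode is not in the AE listing, it is absent from all four tables. If a patient's first episode is coded under one term and the second under the other, a row for neutropenia alone would date first onset from the second episode, lose the recurrence, and report the wrong episode's duration.

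**Working it through.** **Step 1. Does any planned output apply the SAP 5.2.3.1 rule?**

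| Planned output | Source | Why it does not apply the rule |
|---|---|---|
| Tables 14.3.1.10, .12, .14, .16 | AE listing 16.2.23 | Reported terms; no ANC criterion |
| Table 14.3.1.2 | AE listing 16.2.23 | Counts patients by term; no ANC criterion |
| ANC values and changes | Hematology listing 16.2.9 | Means by visit |
| ANC shift tables | Hematology listing 16.2.9 | Baseline against last assessment, low/normal/high; a resolved episode disappears |
| Proportion with abnormal ANC (SAP figures, Hematology) | Not stated | One assessment at a time; no 1.5/1.0/0.5 categories |
| Out-of-range incidence (SAP 6.3.4) | Not stated | Protocol 9.4.1.4 requires two consecutive measures; the SAP drops that condition |

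None applies the confirmed categories. Scheduled counts are weekly at the closest, so the repeat within 3 days will usually be an unscheduled count, for which the by-visit shells have no row. Scheduled draws between visits may go to a local laboratory (Protocol 7.2.2). SAP 16.2 gives these data their own listing, "16.2.25 Listing of local labs", which no table shell cites.

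**Step 2. How can a confirmed case escape the neutropenia row?** It may be marked not clinically significant and never enter listing 16.2.23, or it may enter as neutrophil count decreased. SAP 6.3.4 lists no preferred terms to pool.

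**Step 3. How much could the second route matter?** Inputs are the Protocol 1.3 counts among 712 patients. The stated percentages reproduce:

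- Neutropenia: 49/712 = 6.88% (stated 6.9)
- Agranulocytosis: 15/712 = 2.11% (stated 2.1)
- Neutrophil count decreased: 50/712 = 7.02% (stated 7.0)

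Overlap between terms is not given, so only bounds are possible.

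*Two terms.* Patients with either neutropenia or neutrophil count decreased number between 50 (full overlap, 50/712 = 7.0%) and 49 + 50 = 99 (no overlap, 99/712 = 13.9%). Neutropenia alone misses 1/50 = 2% to 50/99 = 51% of them.

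*Three terms*, since the tables also name agranulocytosis. Let U be the patients with neutropenia or agranulocytosis: from 49 (all 15 inside the 49) to 49 + 15 = 64. Let x be the patients with neutrophil count decreased only: from max(0, 50 − U) to 50. The share missed is x/(U + x).

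- Minimum: U at least 50 and x = 0, giving 0%
- Maximum: U = 49 and x = 50, giving 50/99 = 51%
- All three terms disjoint: 50/(64 + 50) = 50/114 = 44%

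*Scale.* Assume the same rates and 100 to 300 enrolled, 300 being the parent study's planned total. Neutropenia would be expected in about 7 to 21 patients (100 × 49/712 = 6.9; 300 × 49/712 = 20.6), neutrophil count decreased in about 7 to 21 (7.0; 21.1), and agranulocytosis in about 2 to 6 (2.1; 6.3).

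Nothing in the documents quantifies the first route, the clinical-significance judgement.

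**The case against.** **The shells are not binding and the list is open.** SAP 17 says tables may differ from the shells, and the special-interest list is introduced with *such as*, so nothing forbids adding neutrophil count decreased. That is true. However, an open list leaves the grouping to whoever programs the table, and no text points to ANC as the source.

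**ANC is analysed, and every AE term is reported.** Neutrophil count decreased will appear in Table 14.3.1.2, and ANC has its own tables and figures. This stands: the incidence of each reported term is not lost. What those outputs do not give is confirmed episodes by category, with onset, recurrence and duration.

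**Local counts may already be in listing 16.2.9.** The hematology shells have weekly rows for Weeks 1 to 51, when draws may be local. The documents do not settle this. The absence of a citation to listing 16.2.25 leaves the question open and does not prove exclusion.

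**Severe cases are hard to lose.** A reader might infer that agranulocytosis would be missed. The documents do not support that: it is named in all four tables, confirmed ANC below 0.5 requires withdrawal (Protocol 4.5), and blood dyscrasias are an SAE example (Protocol 7.2.1.5). Moderate neutropenia requires treatment interruption, so a not-significant mark is most plausible for brief mild episodes.

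**Intensity and symptoms.** Because "Intensity refers to the degree of discomfort or impairment associated with an event", a reader might infer that the special-interest tables under-grade symptom-free cases or omit them. The four tables have no intensity column. Intensity enters the worst-severity summary and the severe-AE row of Table 14.3.1.1, and the CTCAE scale is recommended alongside, so under-grading there is only a possibility. Protocol 7.2.1.1 requires no symptoms for a laboratory AE.

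**The pooled counts are a weak guide.** They are at least possibly related reactions from other trials, and neutrophil count decreased may include unconfirmed single counts. This stands; the counts are illustrative.

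**Conclusion.** The definition in SAP 5.2.3.1 is not connected to the special-interest tables, and no other planned output applies it. Confirmed mild and moderate neutropenia may be missed, or its first onset, recurrence and duration mis-stated.

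The size is not determinable from the documents. Omitting neutrophil count decreased would cost from about 0% to 51% of patients with a related term, assuming the Protocol 1.3 counts carry over and leaving overlap unknown. It would be wrong to read this as half the cases being lost: 51% is the extreme at which neutropenia and neutrophil count decreased never share a patient and every agranulocytosis patient also carries the neutropenia term. The change should be made, because it serves the primary objective and uses data already collected.

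**What to change.** 1. In SAP 6.3.4, add ANC-derived versions of Tables 14.3.1.10, .12, .14 and .16, covering case, worst category, first onset, recurrence and duration. Use all ANC values, central (16.2.9) and local (16.2.25), scheduled and unscheduled.
2. Apply the full SAP 5.2.3.1 rule, including the 3-day confirmation and the third count when categories differ. Cut-offs alone would count isolated low values. Show low counts with no repeat within 3 days on a separate row. State the analysis rule for the end of an episode; Protocol 7.2.1.8.1 gives one for mild cases (two consecutive counts of at least 1.5 x 10^9/L).
3. In the AE-based tables, list the preferred terms and pool neutropenia, neutrophil count decreased and agranulocytosis. Reconcile AE-based and ANC-derived cases patient by patient.
4. Leave investigator-rated intensity in Table 14.3.1.1 as it is, and report worst ANC category in a separate table.

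Cost: SAP wording, and programming to merge local and central ANC. The reported neutropenia rate may be higher than from AE terms alone.
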